**Review of medical records, images, specimens**

The study involves data that exist at the time of IRB submission **and** data that will be generated after IRB submission.

A Feasibility Study Evaluating Mindfulness-Based Intervention Assessing A Wearable Wellness Brain Sensing Device (Muse-S™) in Fibromyalgia Patients.

Study Analysis

NCT04720053

06/24/2024

General Study Information

Principal Investigator: [name];

Co-principal investigators: [name]; [name]

Study Title: A Feasibility study evaluating Mindfulness-Based Intervention Assessing A Wearable Wellness Brain Sensing Device (Muse-S™) in Fibromyalgia Patients.

Protocol date of most recent review and approval: 24 June 2024

Data Analysis

Data Analysis Plan:

Demographic characteristics are described using mean and standard deviations or frequencies and percentages based on the type of variable. Differences in WPI and perceived stress were reported as baseline minus the end of study (day 90) value. A linear mixed model with repeated measures for each time point that WPI was taken will be utilized to estimate the association between percent of time spent in calm state with the WPI outcome. For each time interval, the percent of time spent in a calm state will be calculated by taking the average of the calm percentage during the interval. Age, sex, and the total amount of meditation time at each interval will also be adjusted for in the model.

Endpoints:

Primary Hypothesis: With an increase in the percentage of time spent in calm state, the WPI and perceived stress will be lower.

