### Aims, purpose, or objectives:

1. To study the feasibility of a wearable brain sensing wellness device to provide mindfulness training to fibromyalgia patients.
2. To assess the association between duration of active state and calm state as measured by the Muse-S™ Headband System, and quality of life (QOL), subjective stress, sleep, and pain in fibromyalgia patients.

The primary outcome will be the change in wide pain index (WPI) and stress over time.

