## Study Design and Methods

### Methods:

All study participants will receive the Muse S™ Headband system and will be asked to use the program daily.

We will assess the following:

- Changes in QOL, sleep, stress, and WPI
- These changes will be measured through week 2, month 1, month 3 and month 6.

	Consent /screen /baseline	Treatment Phase				Follow up Phase
		1	2	3	4	
Visit Type	Face to Face	Phone/ email	Phone/ email	Face to Face/phone/ email	Face to face/phone/ email	
Visit Days	0	14	30	90	180	
Informed Consent	X					
Inclusion/Exclusion	X					
Demographic and History Form	X					
Numeric Pain Intensity Scale (NPIS)	X	X	X	X	X	
Center for Epidemiology Studies Depression (CES-D)	X			X	X	
Widespread Pain Index (WPI)	X			X	X	
Linear Analogue Self-Assessment (LASA - QoL)	X	X	X	X	X	
Stress Scale (PSS)	X	X	X	X	X	
Pittsburgh Sleep Quality index (PSQI)	X	X	X	X	X	
Satisfaction Survey (WIWI)						X
Adverse Events 		X	X	X	X	
Concomitant Medication 	X	X	X	X	X	
Instructions for Muse-S™	X					
End of Treatment/End of Study Forms					X	X

**1** = For visit 5, only serious adverse events will be newly collected; **2** = For visit 5, only newly added concomitant medications for fibromyalgia symptoms will be collected

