### Study Visit Windows:

Each visit will have a window from midpoint of prior visit to midpoint of latter visit.

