### Assessments:

#### *Safety:*

- CES-D (Center for Epidemiological Studies – depressed Mood Scale): A validated and frequently used self-report measure of depressive symptoms.

*Outcomes:*

- Demographics Form: This form collected demographic and other lifestyle history of the research subject.
- Linear Analogue Self-Assessment (LASA): A six-item measure of quality of life (QOL), in which QOL is conceptualized as a multidimensional construct with five domains (physical, functional, emotional, spiritual, and social). This data will be collected at screen (prior to any treatment), day 14, day 30, day 60, end of treatment day 90, and at end of study day 180 (6 months post last treatment).
- Stress: Will be evaluated through the Perceived Stress Scale (PSS). The PSS is a 10-item Likert scale that measures global life stress by assessing the degree to which experiences are appraised as uncontrollable or unpredictable. Scores can range from 0 to 40, with higher scores indicating greater perceived stress. Reliability is reported as 0.85, with Cronbach alphas ranging from 0.75-0.86.
- Widespread Pain Index (WPI): defined as a 4-quadrant plus axial pain, measuring widespread pain in 19 specific places on both sides of the body, above and below the waist. This data will be collected at screening, end of treatment day 90, and at the end of study day 180 (6 months post last treatment).
- Numeric Pain Intensity Scale (NPIS): 0-10 pain assessment scale. Participants rate their pain on a scale of 0 to 10. Zero means “no pain,” and 10 means “the worst possible pain”.
- Sleep Quality: *The Pittsburgh Sleep Quality Index (PSQI)* is an effective instrument used to measure the quality and patterns of sleep in adults. This is a 9-item, likert scale, validated, scoring system. It differentiates “poor” from “good” sleep quality by measuring seven areas (components): subjective sleep quality, sleep latency, sleep duration, habitual sleep efficiency, sleep disturbances, use of sleeping medications, and daytime dysfunction over the last month.

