### **Subject Retention:**

Participants will not be remunerated for participating in this study, but they will be allowed to keep the Muse-S™ Headbands.

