**Subject Information**

Target accrual: We plan to recruit 43 patients diagnosed with fibromyalgia.

Subject population: A total of 43 adult patients diagnosed with fibromyalgia at Mayo Clinic that meet the following study criteria:

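### The change in WPI and stress is defined only for patients with a day-90 value, so it may differ from the change in all enrolled, and the interim PSS values that could reduce this go unused

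*SAP*

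**What the plan says.** The protocol's aims set the primary outcome: "The primary outcome will be the change in wide pain index (WPI) and stress over time". The SAP's Data Analysis Plan turns this into a paired difference: "Differences in WPI and perceived stress were reported as baseline minus the end of study (day 90) value".

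The schedule table in the protocol's Methods section collects PSS at days 0, 14, 30, 90 and 180. WPI is taken less often. Its entry under Assessments reads: "This data will be collected at screening, end of treatment day 90, and at the end of study day 180". So PSS has two values between baseline and day 90, and WPI has none.

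The SAP's only model is a linear mixed model relating the calm percentage to WPI, adjusted for age, sex and meditation time. It is not presented as the estimate of mean change, and it is not specified for PSS.

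The design has one arm: "All study participants will receive the Muse S™ Headband system and will be asked to use the program daily". On size, the protocol says: "We plan to recruit 43 patients diagnosed with fibromyalgia". Neither document gives an expected dropout rate, an analysis population, a rule for missing day-90 values or a sensitivity analysis.

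The two documents also label the visits differently. The SAP calls day 90 the end of the study. The protocol calls day 90 the end of treatment and day 180 the end of the study.

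**The concern.** A baseline-minus-day-90 difference leaves out every patient without a day-90 questionnaire, whatever that patient reported earlier. A patient who gives PSS at days 0, 14 and 30 and then stops contributes nothing to the reported stress change.

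Some loss is to be expected. Patients are asked to practise daily for three months, and the Subject Retention section says: "Participants will not be remunerated for participating in this study". If those who see no benefit are the ones who stop answering, the mean among the rest will look better than the mean in everyone enrolled. If those who feel better lose interest, it will look worse.

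What is at stake is the primary outcome itself. A reader will take the mean fall in WPI and PSS as the change in the patients who started, and the plan offers nothing that supports or tests that reading.

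**Working it through.** The documents give no effect size, SD, dropout rate or sample-size calculation, so there is no figure of the plan's own to reproduce. Two checks show how far a completers' mean can move. Everything except the 43 and the visit days is an assumption.

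**1. Mixture identity (applies to WPI and PSS alike)**

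Let d be the share of enrolled patients without a day-90 value, and r the mean change in those missing divided by the mean change in completers. Then

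all-enrolled change ÷ completers' change = (1 − d) + d × r.

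Taking the target of 43 as the number enrolled:

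| Missing | d | r = −0.5 | r = 0 | r = 0.5 | r = 1 | r = 1.5 |
|---|---|---|---|---|---|---|
| 4 of 43 | 0.093 | 0.86 | 0.91 | 0.95 | 1.00 | 1.05 |
| 9 of 43 | 0.209 | 0.69 | 0.79 | 0.90 | 1.00 | 1.10 |
| 13 of 43 | 0.302 | 0.55 | 0.70 | 0.85 | 1.00 | 1.15 |

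If those missing did not change at all (r = 0), the completers' mean is 43/39 = 1.10, 43/34 = 1.26 or 43/30 = 1.43 times the all-enrolled mean. At r = 1 there is no bias at any dropout rate. Above r = 1 the completers' mean is too small.

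**2. Simulation for PSS (400,000 patients)**

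Assumed inputs: means 22, 21, 20.5 and 19 at days 0, 14, 30 and 90, so the true fall is 22 − 19 = 3.0; SD 7; correlation 0.6 between visits, except 0.75 between days 30 and 90. The odds of a missing day-90 value are 1.6 or 2.7 times higher per SD of worse change at day 30.

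| Missing at day 90 | Completers' fall, odds ratio 1.6 | Completers' fall, odds ratio 2.7 |
|---|---|---|
| 10% | 3.2 | 3.4 |
| 20% | 3.4 | 3.7 |
| 30% | 3.6 | 4.1 |
| 40% | 3.8 | 4.4 |

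At 20 to 40% missing, the excess over 3.0 is about 0.4 to 1.4 points.

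- *Reverse pattern.* With better responders more likely to be missing (odds ratio 1/1.6), the completers' fall is 2.6 at 20% missing and 2.2 at 40%, which is an understatement.
- *Using the earlier visits.* Regressing day 90 on days 0, 14 and 30 and averaging over everyone returns 3.0. This follows from the set-up, because missingness there depends only on values the regression uses.
- *When that assumption fails.* If missingness depends on the day-90 change itself, with the same two odds ratios, the same method returns 3.3 to 3.6 at 20% missing and 3.6 to 4.1 at 40%. Only part of the bias is removed.

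**3. Does the planned model already cover this?**

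No. Its target is the slope of WPI on calm percentage, not the mean change, and PSS has no model. It also needs an average calm percentage for each interval, which cannot be formed for a patient with no sessions in that interval.

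**The case against.** The strongest objection is that nothing in the documents shows a bias. They report no attrition and no results, and with complete day-90 data the completers' mean is the all-enrolled mean. This stands. A reader might infer that the plan's figure overstates the benefit. That needs missing patients to have improved less than completers, which is plausible but stated nowhere, and the reverse pattern changes the sign.

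The protocol also takes steps that limit loss. Day 90 can be done by telephone or online, questionnaires can go by email link or be completed by telephone interview, and the window is wide: "Each visit will have a window from midpoint of prior visit to midpoint of latter visit". For day 90 that runs from (30 + 90)/2 = day 60 to (90 + 180)/2 = day 135. Patients also keep the headband, although the protocol does not say whether this depends on completing the study. Missing rates of 20 to 40% may therefore be too high, which is why 10% is shown too. These steps reduce the problem but do not say what happens to patients who still have no value.

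A reader might also infer that the lack of a control arm causes the bias. It does not make a completers' mean exceed the all-enrolled mean, and a control arm would not guarantee cancellation, since dropout can differ between arms.

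The protocol speaks of change over time and says of its assessments: "These changes will be measured through week 2, month 1, month 3 and month 6". Interim PSS may therefore be reported in some form. The SAP's definition of the difference still does not use it.

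Finally, this is a feasibility study with no planned test of the difference, and the illustrated bias is modest beside sampling error. The assumed SD of the change is 7 × √(2 × (1 − 0.6)) = 6.26. The standard error is then 6.26/√34 = 1.07 with 34 completers and 6.26/√26 = 1.23 with 26. The bias is below one standard error in most scenarios. That limits the importance of the point, but the standard error describes sampling error only and does not show a shift from selective loss.

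**Conclusion.** The point holds in a limited form. As defined, the change in WPI and PSS is a completers' figure. It may differ from the change in all enrolled, and it ignores PSS data already collected from patients who later go missing. An upward difference is plausible but not certain, and the documents fix neither its sign nor its size.

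The illustrated range, 3.2 to 4.4 against a true PSS fall of 3.0 at 10 to 40% missing, rests wholly on the assumed means, SD, correlations, dropout rates and odds ratios. For WPI there is only the mixture identity.

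Nor should a reader infer that a model on all visits would recover the true change. It does so only if missingness depends on observed values. It is still the better estimate, because it uses the available data and makes its assumption explicit.

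**What to change.** In the SAP's Data Analysis Plan:

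1. Estimate the day-90 PSS change from a repeated-measures mixed model on all available PSS values (days 0, 14, 30, 90 and 180), including patients without a day-90 value.
2. Estimate the WPI change in the same way from days 0, 90 and 180. WPI has no interim visit, so a patient lost before day 90 contributes only a baseline value, and the gain is smaller than for PSS.
3. State that both estimates rely on missingness depending on observed values, and that otherwise only part of any bias is removed.
4. Add a sensitivity analysis that sets the change to zero in patients without a day-90 value. The denominator should be the number actually enrolled; 43 is the accrual target.
5. Report the number of patients with data at each visit.
6. Reconcile the SAP's and protocol's use of the term end of study, so that it is clear which visit enters the difference.

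The cost is a few sentences in the SAP and modest extra analysis, with no new data collection. The headline change may come out less favourable.

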- Satisfaction with the program: *Was it Worth it Questionnaire (WIWI)* This satisfaction survey will be administered to the participants after completing intervention and at the end of the study, probing their satisfaction with the research study. These data could be used to assess the feasibility of the intervention by asking the patient if the entire research experience was worth it for them.

*Adherence to Intervention:*

- Adherence to the Muse-S™ will be assessed by de-identified data available within the cloud, provided by InteraXon. InteraXon only has information per subject through subject ID only (as was provided by Mayo Clinic site), so when the cloud data is provided to Mayo, it will be linked to each subject through their study ID.

*Intervention:*

[figure not shown]
- The Muse-S™ Headband system:

The Muse-S™ Headband system is a brain sensing headband that measures brain activity by detecting electrical impulses created by the brain. The Muse-S™ Headband system uses a series of focus attention training methods to train the brain. Each focus attention session takes approximately a minimum of 5 minutes, and has been shown to reduce stress, anxiety, and improve focus and productivity. The Muse-S™ Headband system has seven sensors with four channels of EEG data for an accurate, high-quality experience. The battery life is approximately five hours and uses an industry-standard micro-USB charger. Forty Muse-S™ Headband systems will be provided by the manufacturer at no cost in support of this study.

Use of Muse-S™ Headband systems will be demonstrated to each participant prior to their first mindfulness practice session, which will be completed during the baseline visit with the study coordinator. The study coordinator will present the participant with detailed instructions on how to begin each session. The frequency of the sessions thereafter will be at the participant's discretion according to the study's requirements (daily practice). Mindfulness training will follow the protocol in the Muse-S™ app, which follows a standard breathing exercise with EEG brain state feedback through the mobile device, as designed by a panel of experienced mindfulness practitioners. In short the Muse-S™ is a *FitBit* like device for the brain.

The study participants can access 3 different types of meditation while using the Muse-S™ Headband system. They are as follows:

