- **Server Data:** As the patients complete the 10 minute sessions, the information from these sessions will be uploaded to the Muse-S™ secure cloud servers hosted by Google. Individual subject data will be visible to each subject at the end of each session, and data from the previous session stored in the "me" tab in the app. Study organizers will have ongoing access to each subject's data to monitor compliance and performance. These data can include the study-specific identification number, gender, and age of the subject, the time and duration of each session, EEG data, heart rate (PPG) data, and the performance ('percent calm') score per session. Interaxon's privacy policy, which can be found at [www.choosemuse.com/privacy](http://www.choosemuse.com/privacy) will apply to Interaxon's use of the subjects' data. In order to maximize protection of the individual's privacy, the study organizers will ensure that the subjects are assigned anonymized email address and names for use in the Muse -S™ application and when contacting the Muse-S™ customer support. To ensure that no health

data is shared with Interaxon, the study organizers have agreed to ensure that no health data will be shared with Interaxon.

- Additionally, the data will be made available for aggregate download by specific members of the research team, from a secure server at regular intervals until and shortly after the study's conclusion. The study coordinator may view the patient's activity via a web browser.  
The Muse-S™ steps include: 1) Open the Muse-S™ App on your phone. 2) select meditation type 3) if meditating with the headband, turn on the Muse-S™ headband. It will pair via Bluetooth to the app 4) put on headband (if doing a meditation with headband) 5) meditate for minimum of 5 minutes or longer 6) add any journal or mood entry if desired 7) review results.
- Cleaning the Muse-S™: Each patient will be given a brand new, out-of-the-box Muse-S™ Headband system. If cleaning must occur, the entire Muse-S™ including the head set can be wiped down with a standard disinfectant wipe. The band can also be hand-washed gently with soap and water. The module on the band is not waterproof but can be wiped with disinfectant.

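### Must the SAP weight percent calm by session minutes, and list the eligible sessions, before its main exposure can be read as percent of time?

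*SAP*

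**What the plan says.** The SAP's Data Analysis Plan fits a linear mixed model of WPI on the percent of time in calm state. The primary hypothesis names the exposure in the same way. For each interval, "the percent of time spent in a calm state will be calculated by taking the average of the calm percentage during the interval". The covariates are age, sex and meditation time: the "total amount of meditation time at each interval will also be adjusted for in the model".

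The Protocol's Server Data item lists what the manufacturer can supply, including "the time and duration of each session, EEG data, heart rate (PPG) data, and the performance ('percent calm') score per session". Score and duration are therefore both available per session.

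Session length is described in three places:

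- Server Data, opening sentence: "As the patients complete the 10 minute sessions"
- Server Data, list of steps: "meditate for minimum of 5 minutes or longer"
- Intervention: "Each focus attention session takes approximately a minimum of 5 minutes"

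The Intervention section offers three meditation types, and the Go-to-sleep type may be followed by overnight wear. The steps also allow meditation without the device: "put on headband (if doing a meditation with headband".

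**The concern.** The exposure is named as a share of time but appears to be computed as an average of scores. If a patient is calmer in long sessions than in short ones, the simple mean understates the share of time spent calm; if calmer in short sessions, it overstates it. The coefficient of interest is the slope on this variable, so a mismatch would make it a slope per point of mean session score, which is not what the hypothesis states. Adjusting for total meditation time does not help, because it does not reweight sessions within an interval.

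The set of sessions is also unstated. Headband-free sessions could add minutes to the covariate without contributing to the exposure. A long sleep recording, if it were scored, could matter a good deal. Two analysts might then build different variables from one download.

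**Working it through.** The documents give no exposure values, no distribution of session lengths or scores, and no power calculation behind the target of 43 patients. There is no planned figure to reproduce, so the check compares the two definitions directly.

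**Identity.** With session minutes d and session percent calm c:

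- simple mean = Σc / n
- time-weighted value = Σ(d·c) / Σd
- difference (weighted − simple) = cov(d, c) / mean(d) = r × SD(c) × CV(d)

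Arithmetic check: 5 minutes at 80% and 30 minutes at 20% give (5×80 + 30×20)/35 = 28.57 against a simple mean of 50, a difference of −21.43. The formula gives −375/17.5 = −21.43.

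**Equal sessions.** If every session lasts 10 minutes, CV(d) = 0 and the difference is 0.

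**Ordinary variation in length (assumed).** Session length is uniform from 5 to 15 minutes (CV 0.289) up to 5 to 60 minutes (CV 0.489), within-patient SD of the score is 15 to 20 points, and r is 0.1 to 0.5.

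- smallest difference: 0.1 × 15 × 0.289 = 0.43 points
- largest difference: 0.5 × 20 × 0.489 = 4.89 points

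A shift common to all patients moves the intercept and leaves the slope alone, so these figures do not measure harm to the main result.

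**Effect on the slope.** The slope changes only if r rises or falls with a patient's own calm level. Assume a between-patient SD of 12 points, a within-patient SD of 15, a patient-specific r with SD 0.3, and a correlation (link) of ±0.6 between r and mean calm. Then approximately

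slope ratio = 1 + link × (SD of r / between-patient SD) × SD(c) × CV(d)

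- 5 to 15 minutes: 1 ± 0.6 × (0.3/12) × 15 × 0.289 = 1 ± 0.065
- 5 to 60 minutes: 1 ± 0.6 × (0.3/12) × 15 × 0.489 = 1 ± 0.110

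Simulation with 20,000 patients and 60 sessions each agrees:

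| Session length | Link | Slope ratio |
|---|---|---|
| 5 to 15 min | none | 1.00 |
| 5 to 15 min | ±0.6 | about 1.06 / 0.94 |
| 5 to 60 min | none | 1.00 |
| 5 to 60 min | ±0.6 | about 1.10 / 0.90 |

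Across these settings the two versions correlate at 0.98 to 0.999.

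**Against sampling error.** The SAP states no power or significance level. If the slope were just detectable with 80% power at a two-sided 5% level (assumed), slope/SE would be about 1.96 + 0.84 = 2.8. A 10% change is then 0.28 SE and a 6% change 0.17 SE.

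**One very long session.** The Intervention section says "The battery life is approximately five hours", so take one 300-minute session added to 29 ten-minute sessions at an assumed 35%.

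| Score in long session (assumed) | Simple mean | Time-weighted |
|---|---|---|
| 50% | 35.5 | 42.6 |
| 65% | 36.0 | 50.3 |
| 80% | 36.5 | 57.9 |

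For the last row, (29×35 + 80)/30 = 36.5 and (290×35 + 300×80)/590 = 57.9. The long session carries 300/590 = 51% of the weight in the time-weighted version and 1/30 = 3.3% in the simple mean.

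**The case for a change.** The best argument for a change is that the exposure in the SAP's only model should not be open to two readings, and that two or three sentences would settle it at almost no cost. The identity is exact, the protocol does not guarantee equal session lengths, and the list of eligible sessions matters whatever the weighting. All of that is true, and a sentence naming the averaging unit would be tidy.

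It does not amount to a required change, for four reasons.

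- The mismatch is inferred. The SAP says neither per-session nor unweighted, and an average over time also fits its sentence.
- Weighting delivers percent of time only if the device score is itself a fraction of session time. The Protocol calls it a performance score and does not define it.
- Equal weight per session is a sound choice when daily practice is what patients are asked to do. Describing the result as a mean session percent-calm score would be just as coherent.
- The session question largely answers itself. Without the headband there is no EEG and so no calm score to average, and total meditation time is a separate covariate that need not cover the same sessions. Session type is not among the listed data, so a rule by type might not be workable.

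The long-recording case is the only one with large numbers. The documents do not establish that such recordings are scored, and it is the weighted version that they would distort.

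**Conclusion.** No change to the plan. This is an unstated detail in a feasibility study's SAP that an analyst can settle from the collected data, and the choice of weights is a fair trade-off. For ordinary sessions the two definitions rank patients almost identically. The slope ratio is 1.00, moving to about 0.90 or 1.10 only under an assumed link between the length-calm relation and a patient's calm level. The simple mean is the sturdier of the two if a very long session appears.

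These sizes rest on assumed session lengths, score SDs and correlations, since the documents give none. The conclusion would need another look only if long sleep recordings proved to be both scored and common. When reporting, the analyst should describe the exposure as it was actually computed; that is normal good practice and needs no amendment.

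### The WPI mixed model names neither visit nor baseline WPI and leaves the baseline row undefined, so what the calm coefficient measures depends on an unstated choice

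*SAP*

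**What the plan says.** The SAP's Data Analysis Plan states: "A linear mixed model with repeated measures for each time point that WPI was taken will be utilized to estimate the association" of percent calm with WPI. The exposure is defined per interval: "For each time interval, the percent of time spent in a calm state will be calculated by taking the average of the calm percentage" over that interval. The adjustment set is "Age, sex, and the total amount of meditation time at each interval will also be adjusted for in the model". No visit effect, baseline WPI term or covariance structure is given. Baseline WPI appears by name only in a descriptive sentence: "Differences in WPI and perceived stress were reported as baseline minus the end of study (day 90) value".

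The Protocol (Assessments, WPI) fixes the measurement times: "This data will be collected at screening, end of treatment day 90, and at the end of study day 180". The device supplies "and the performance ('percent calm') score per session" (Server Data). The Intervention section places the first practice session at the baseline visit, so no practice interval comes before the baseline WPI. The intervention is requested for the first three months (Treatment phase). After that, participants are not asked to continue, "but they will be allowed to keep the Muse-S™ Headbands" (Subject Retention). The listed app steps include "if meditating with the headband, turn on the Muse-S™ headband", so a session can also be done without it.

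**The concern.** The SAP's primary hypothesis rests on the calm coefficient in a single-arm study of 43 patients. Two analysts following this text could fit materially different models.

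- **Baseline row left out.** Percent calm is an average over sessions and is undefined before any session, so this is a natural reading. The model then relates WPI level to calm, and baseline WPI goes unused although the Protocol's primary outcome is change. Patients who start less affected may also be calmer, and calm and WPI may drift together between days 90 and 180.
- **Baseline row kept.** The phrase about each time WPI was taken supports this too. Calm would come from the baseline-visit session or be set to 0%. With no visit term, any before-after improvement is then available to be attributed to calm.

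An interval after day 90 may also contain no headband session, and no rule covers that.

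**Working it through.** The documents give no SD, correlation, effect size or test level, so there is no figure to reproduce.

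**Inputs.** From the documents: n = 43; WPI at baseline, day 90 and day 180. Assumed: WPI SD 4 (variance 16); within-patient correlation 0.6, giving patient variance 9.6 and residual variance 6.4; calm in units of 10 points, patient SD 1.0 and interval SD 0.8; two-sided 5% test. The large-sample arithmetic below ignores age, sex and meditation time. The simulations (2,000 trials per cell unless stated) include them.

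**1. Row left out: precision.** A random-intercept slope pools a between-patient and a within-patient part, each weighted by its information per patient.
- Variance of a patient's mean calm = 1 + 0.64/2 = 1.32.
- Between weight = 2 × 1.32 / (6.4 + 2 × 9.6) = 0.103. Within weight = 0.64/6.4 = 0.100.
- SE = 1/√(43 × 0.203) = 0.338. Simulated: 0.344.
- Given baseline WPI, patient variance falls to 9.6 × (1 − 0.6) = 3.84, and the between weight becomes 2.64/(6.4 + 7.68) = 0.1875.
- SE = 1/√(43 × 0.2875) = 0.284. Simulated with baseline and visit: 0.296.
- Simulated ratio 0.344/0.296 = 1.16. Over 180 assumption sets the excess is 7-35%, driven mainly by the within-patient correlation. Visit alone does not improve precision (0.346).

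**2. Row left out: severity.** No calm effect; correlation of patient-level calm with severity −0.3.
- Covariance = −0.3 × 1 × √9.6 = −0.930; between slope = −0.930/1.32 = −0.704.
- Pooled: −0.704 × 0.103/0.203 = −0.36. Simulated: −0.354.
- With baseline WPI: covariance −0.930 × 0.4 = −0.372; calm variance 1.32 − 0.864/16 = 1.266; slope −0.294; weight 2.532/14.08 = 0.180. Pooled: −0.294 × 0.180/0.280 = −0.19. Simulated with both terms: −0.187.
- Simulated share removed: 34%, 48% and 61% at within-patient correlation 0.4, 0.6 and 0.8.

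**3. Row left out: joint drift.** No calm effect, meditation time constant.
- Calm +10 and WPI −2 from day 90 to 180: within sum of squares 0.64 + 1/2 = 1.14; within slope (1 × −2/2)/1.14 = −0.877; weight 1.14/6.4 = 0.178. Pooled: −0.877 × 0.178/0.281 = −0.56. Simulated: −0.546; baseline term only −0.426; visit term 0.00.
- Calm +5 and WPI −1: simulated −0.18, or −0.11 if meditation time falls to 40%.

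**4. Row left out: general improvement alone.** Rejection is about 5% with or without the added terms.

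**5. Row kept, calm from the baseline-visit session.**
- Between weight = 3 × (1 + 0.64/3)/(6.4 + 3 × 9.6) = 0.103; within weight = 1.28/6.4 = 0.200. SE = 1/√(43 × 0.303) = 0.28, no worse than in step 1 with both terms.
- Now let WPI improve by 2 points after baseline and calm rise by 5, with no calm effect. Within sum of squares = 1.28 + 0.25 × 2/3 = 1.447; cross-product = 0.5 × −2 × 2/3 = −0.667; slope −0.461; weight 0.226. Pooled: −0.461 × 0.226/0.329 = −0.32. Simulated (150 trials): −0.29, rejection 17%. A visit term returns it to nominal.

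**6. Row kept, calm coded 0%, no visit term.** Simulated rejection is 22% for a 1-point and 67% for a 2-point general improvement, and 4% with visit. A separate simulation (calm SD 15, WPI falling 1.5 points per visit) gave 82%, and 7% with visit.

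**The case against.** The strongest reply has four parts.

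1. **The literal text puts a row at every WPI time, baseline included, and a baseline-visit session exists to supply a calm value. Precision is then not lost.** This stands: step 5 gives 0.28. The severity contribution is also smaller on that reading, −0.28 by simulation against −0.35. It does not rescue the plan, because it is the reading under which general improvement leaks into the coefficient unless visit is in the model. The SAP also does not say that this session is used.
2. **The plan claims only an association, so severity is not an error.** Largely accepted. It is confounding to reduce and disclose, and one baseline WPI removes only about half of it.
3. **The larger drift is implausible once the intervention is no longer requested.** Fair. Nothing in the documents supports that size, and the moderate drift gives rejection of only 8%, or 6% if use falls.
4. **Baseline as a covariate is a preference.** Also fair. Keeping it as an outcome with visit terms performs as well: SE 0.270 against 0.273 in the separate simulation at within-patient correlation 0.5.

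A reader might also infer from the SAP's day-90 end-of-study label that the model has one post-baseline row per patient. The text does not support this. The label qualifies the descriptive difference only, and the model sentence sets its own rows.

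**Conclusion.** The point holds, conditionally, and should be fixed. The SAP does not determine the model, and each available reading has a defect that a visit term, a single stated use of baseline WPI, or both would reduce.

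- Row left out: SE about 0.34 against 0.30, with possible contributions from severity (about −0.35 per 10 calm points at a correlation of −0.3) or from joint drift.
- Row kept without visit: no precision loss, but general improvement can generate the association under 0% coding or when calm rises after the first session.

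Two stronger readings are tempting and unsupported. One is that general improvement necessarily makes the calm result spurious; with the baseline row left out, rejection stays near 5%. The other is that precision is lost whatever the analyst does; it is not if the row is kept.

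The SDs, correlations and drifts are all assumed, and rejection rates move with them: severity at −0.3 gives 18% under the inputs above and 30% under the separate simulation's inputs. The figures show direction, not expected size.

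**What to change.** Amend the SAP as follows.

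1. Add categorical visit as a fixed effect and state the patient random intercept.
2. Use baseline WPI in exactly one way: (i) as a covariate, with days 90 and 180 as outcomes, which is simplest; or (ii) as an outcome row with visit terms and no baseline covariate. Under (ii), state either that the calm and meditation-time terms apply only after baseline or that the baseline-visit session supplies them.
3. Do not treat absent calm as an observed 0%. Set percent calm to missing for an interval with no headband session, and report the number by visit.
4. Report the result as an association with residual confounding by severity. Splitting calm into patient mean and within-patient deviation is an optional sensitivity analysis. It removes stable severity from the within-patient coefficient, but its SE is 0.50 against 0.30.
5. Separately, reconcile the end-of-study label (day 90 in the SAP, day 180 in the Protocol), which governs the descriptive difference.

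The cost is SAP wording and about two degrees of freedom, with data already collected. If analysis has begun, label the revised model post hoc. Dropping no-session rows costs some precision (SE 0.30 to 0.34 if half of the day 90-180 values are missing) and selects on adherence. If absence is linked to both low calm and high WPI, with 30-50% missing, a true −1.00 is estimated as −0.91 to −0.96. A day-90-only model with baseline WPI avoids that selection, at SE 0.41, and would serve as a sensitivity analysis.
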